 End of Intervention (3 months) and 6 month interview completed outside of -14/+14 day window
 Caregiver does not complete all 6 sessions within 4 1/2 months

RECRUITMENT

Caregivers will be recruited from the MS clinic and inpatient unit as Veterans are admitted or seen. We are requesting a waiver of informed consent and HIPAA authorization for recruitment purposes only, as a method of recruiting Veterans who have been diagnosed with MS, prior to participation in the study. Privacy risks to research subjects will be minimal. We will mail brochures to eligible Veterans. Veterans and/or Caregivers may contact us if they are interested in participating. If we do not hear from the Veteran and/or Caregiver in a reasonable amount of time after mailing the brochures, we will telephone the Veteran to give him/her more information about the study. The MS Clinic meets one day a week and study staff will be present to provide information and to screen Caregivers and Veterans. However, Veterans with MS are only seen in the MS clinic every three to six months, thereby potentially missing the enrollment period. Brochures will be mailed to all eligible participants. Brochures will also be strategically positioned around the hospital as well as in the MS clinic. Clinicians in the MS clinic will aid in the identification of eligible Veterans. Full informed consent and HIPAA authorization will be collected after screening as part of study enrollment. Our consent process for Caregivers and Veterans is overseen by the VAMC Memphis IRB and Research and Development Committee.

Screening. Participants must give permission to the Research Associate to be screened after hearing a study description that includes information about the research study and the screening process itself. Research study information includes a statement of the research (purpose, procedures), reasonably expected benefits to subjects or others, and costs. Screening process information includes duration of screening, alternatives, extent of confidentiality, and authorization for release of protected health information for research purposes.

Caregiver Consent and Veteran Consent. After screening, consent forms are provided to the Caregiver and Veteran participant. All participants must give written informed consent before becoming study participants and both Caregiver and Veteran must agree for the Caregiver to participate.

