- If the Caregiver does not complete the REACH VA MS intervention by 4 ½ months, the Program Coach will stop the sessions, and let the data collector know to go ahead and contact the Caregiver to complete the follow-up interview (End of intervention/3 month). Program Coach will complete a Protocol Variation form and check the box beside Caregiver did not complete all 6 sessions with 4 ½ months under Intervention.

Informed Consent Flow Chart

Confidentiality. Although the information collected by this study is considered to have low potential for abuse because the data do not address sensitive issues, appropriate safeguards are established. Data, other than demographic information, use only ID numbers as identifiers. Paper forms of the research records are kept in secure locked files in the project area, Building 1/Administration Building, Room BEG-16, in a secured building only accessible to project staff. Persons other than research personnel may not obtain files. Research personnel no longer working on the study will not have access to study data. Electronic data is stored on a VA server folder that only local VAMC project research staff can access, P:\Documents\151\Investigator Folders\[name]\855122. All computers are password protected. Audiotapes are stored in locked file cabinet in building that is access limited to project staff. ID numbers are kept in a different locked file cabinet in the Building 1/Administration Building, room BEG-16. The staff is trained in all ethics and confidentiality standards.

Project Staff will have access to the information. Representatives from the Memphis Institutional Review Board (IRB) are eligible to review research records as part of their responsibility to protect human volunteers in research.

The health care professionals involved in this research have the legal responsibility to report suspected cases of abuse, neglect, or exploitation to the appropriate legal authorities.

Risk/Benefits Assessment. It is anticipated that the caregiver will experience more benefits than risks from participation in this study. Risks to research subjects will be minimal, but may include fatigue or distress from answering questions.

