The participant may not benefit directly from their participation in this study. However, there may be a benefit to society, in general, from the knowledge gained in connection with your participation in this study. Taking part in this study may help participants better understand the problems they may be having caring for Veterans with MS. Any information obtained from this research study and which may be important to your health will be shared with the participant.

Withdrawal from the Protocol. The participant may discontinue participation in the research at any time without penalty or loss of rights to which the participant is entitled. If a participant withdraws from the study, the participant will be asked to complete a discontinuation data collection questionnaire over the phone and will not be contacted by the research staff in the future. During the course of the study, if the veteran exhibits threatening behavior toward the caregiver because of participation in the study, the Principal Investigator has the right to withdraw the caregiver from the study. This is included in the consent form under the section, Investigator-Initiated Termination of Participation. If either participant wishes to withdraw, the other participant may elect to continue with the study without the other. For example, if the Veteran wants to withdraw from the study, but the Caregiver does not, the Caregiver may continue with the study. The Veteran will be withdrawn. However, if the Veteran no longer wants to participate and also doesn't want the Caregiver to participate in the study, the Caregiver and Veteran will both be withdrawn.

Copy of the Approved Informed Consent

- Always use the original ([name]'s Office), not the copy in the MOP for making the necessary copies of the consent form for the Caregivers and Veterans.
- Be sure to check the expiration date on the consent forms.

Copy of the Approved HIPAA Authorization

- Always use the original ([name]'s Office), not the copy in the MOP for making the necessary copies of the HIPAA Authorization for the Caregivers and Veterans.
- Be sure to check the expiration date.

RETENTION PROCEDURES

Retention Procedures

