Follow-up interview reminder reports are available as needed from Access. These reports list the Caregivers/Veterans who are due for their follow-up data collection visits and the date interval for their next visit. This information is also available on each of the individual recruitment form records in Access.

All Caregivers/Veterans get phone reminders prior to their scheduled data collection telephone calls. If the appointment has been rescheduled at the time of the phone call or face to face interview, then the new data collection date is obtained and recorded on the Main Calendar. An additional reminder phone call is made prior to the new data collection call.

All missed appointments are followed within 24 hours by a phone call or email to the Caregiver/Veteran who is then encouraged to reschedule the appointment. If the Caregiver/Veteran cannot be reached after three calls on the first and second day, a search will be made after noon on the second day starting with his/her list of contacts. After the Caregiver/Veteran is located, we encourage him/her to reschedule the cancelled data collection appointment or call us back with a convenient date. If the Caregiver/Veteran does not call us back, we will follow-up two days later. If phone attempts fail, we will send a follow-up letter to the Caregiver/Veteran explaining our failure to contact them and the importance of the follow-up interview. An electronic copy of this letter must be filed on the individual Research Associate's P: drive "Failure to contact" folder.

Addresses and phone numbers for the Caregiver/Veteran and his/her contact are updated at all data collection visits. If there is a change in address or telephone number for the Caregiver/Veteran, it is recorded on the Access Recruitment Form by the Research Associate and communicated to others by email so the Program Coach can update her individual data management program.

Incentives for Retention

A number of incentives are built into the study for retention. These may include, but are not limited to the following strategies:

1. an incentive payment (\$25.00/visit) for each completed full data collection visit (baseline, 3, and 6 months);
2. same Research Associate interviewing the participant at each follow-up data collection call;
3. sessions face to face or over the phone for convenience;
4. thank you letter with each payment check sent.

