Paper forms of the research records are kept in secure locked files in the project office. Electronic data is stored on a VA server folder that only local VAMC project research staff can access. After the study is completed, paper data will be stored with other completed research studies in a secured storage area. Records will be maintained and/or destroyed in accordance with the VA Records Control Schedule (RCS 10-1). For electronic information, as stated in the consent form, research information is analyzed for many years after a study, therefore, no specific date can be provided when this information will be destroyed or no longer used.

SCHEDULE OF DATA COLLECTION ASSESSMENTS

Time Frame for Caregiver		
Baseline (Face to Face) After consent signed and before intervention	Second (Telephone or Face to Face) 3 months (+/-14 days)	Third (Telephone or Face to Face) 6 months (+/-14 days)
X	X	X

Time Frame for Veteran		
Baseline (Face to Face) After consent signed	Second (Face to Face) 3 months (+/-14 days)	Third (Face to Face) 6 months (+/-14 days)
X	X	X

MEASURES

Data collection will occur at baseline, End of Intervention (3 months), and 6 months either face to face or by telephone. Data collection will take 30 minutes to an hour, based on face-to-face and telephone data collection in our work with OEF/OIF spouses and soldiers, and stressed caregivers, using the same and similar instruments (Table 3). We have used telephone and face to face batteries of similar length for older caregivers, who have not reported difficulty with these methods of data collection. If interviews completed over the phone, we will send response cards to the participant to make answering more efficient. The same RA will perform all data collection for a participant.

Measures were specifically chosen 1) to capture the mechanisms of action related to the theoretical model for individual stress process, and 2) to map onto measures being used by Multiple Sclerosis clinicians and researchers to provide maximum utility and generalizability for the study results.

If the Veteran/Caregiver team withdraws from the study, we will try to complete an abbreviated program evaluation to determine the reason for withdrawal.

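### A participant who asks to leave gets an exit contact and then no further contact, with no stated option to stop the sessions and keep the 3- and 6-month assessments

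*Combined protocol and SAP*

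**What the plan says.** The combined protocol and SAP describes several ways in which participation can stop.

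- **Withdrawal from the Protocol.** The rule opens "If a participant withdraws from the study"; that person is then "asked to complete a discontinuation data collection questionnaire over the phone and will not be contacted by the research staff in the future". The same section protects the rest of the dyad: "If either participant wishes to withdraw, the other participant may elect to continue with the study without the other". A Veteran who also objects to the Caregiver's participation takes both out, and the investigator may withdraw a Caregiver for safety reasons.
- **Measures.** If the Veteran/Caregiver team withdraws, "we will try to complete an abbreviated program evaluation to determine the reason for withdrawal". No outcome scale is named.
- **Screening and Consent.** A Caregiver who has not finished the intervention by 4½ months falls under a separate rule. The sessions end, and the Coach is to "let the data collector know to go ahead and contact the Caregiver to complete the follow-up interview". The Detailed Project Flowchart lists this event ("Caregiver does not complete all 6 sessions within 4 1/2 months") as a protocol variation.
- **Retention Procedures.** Missed assessments are actively chased: "All missed appointments are followed within 24 hours by a phone call or email to the Caregiver/Veteran".

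Data Analysis plans repeated measures ANOVA of baseline, 3-month and 6-month scores, allows for 15% attrition, and treats an improvement of at least 0.2 SD as clinically significant. It gives no method for missing follow-up scores.

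**The concern.** The plan already accepts, for Caregivers who run out of time, that sessions can end while measurement goes on. It does not extend that choice to someone who asks to leave. Two Caregivers who both stop after session 2 could be handled differently. One who drifts is interviewed. One who says she wants out, and is taken to have withdrawn from the study, answers an exit questionnaire and is not approached again. Her PHQ-9, GAD-7 and Zarit scores at 3 and 6 months are then never requested.

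This matters more than it would in a controlled trial. The result here is a mean change in one group, so there is no comparison arm in which similar losses might partly cancel. Reasons for leaving could well be related to the outcomes. The risk section says session topics and questions may be upsetting, the withdrawal section foresees conflict within the pair, and the Caregiver outcomes are depression, anxiety and burden. Scores that were never requested cannot be recovered by analysis. The first objective, whether the program can be integrated into clinic care, also loses outcome information on participants who chose to leave.

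**Working it through.** **Step 1. The routes side by side.**

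| How participation stops | Section | What follows |
|---|---|---|
| Participant withdraws from the study | Withdrawal from the Protocol | One telephone questionnaire, then no contact |
| The pair withdraws | Measures | Attempt to learn the reason; no outcome scale named |
| One member withdraws | Withdrawal from the Protocol | The other may continue |
| Caregiver has not finished six sessions by 4½ months | Screening and Consent; Detailed Project Flowchart | Protocol variation; sessions stop; end-of-intervention interview still sought |
| Someone asks early to stop the sessions only | Not addressed | Not stated |

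The last row is the gap.

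**Step 2. Inputs.** 25 pairs (Statement of Work, Task 4); 15% attrition and the 0.2 SD mark (Data Analysis); Table 2 effects of 0.3 and 0.4. The leavers' change is not in the documents and is assumed.

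**Step 3. How the plan uses the 15%.** Table 2 can be reproduced with n = (1.960 + 0.842)² × 4(1 − r)/d² ÷ 0.85. For burden at d = 0.3, r = 0.88: 7.849 × 0.48/0.09 ÷ 0.85 = 49.2, rounded up to 50, as stated. All six cells come out as 66/37, 70/40, 50/28 against the stated 66/38, 71/40, 50/29, each within one. The 15% is thus a single allowance for loss, not divided by cause.

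**Step 4. Illustration.** 0.15 × 25 = 3.75, about 4 leavers and 21 completers. Assume all 4 are withdrawals under this rule. With completer change c and leaver change l, in SD units:

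enrolled mean = (21c + 4l)/25

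With l = 0:
- c = 0.20 gives 4.2/25 = 0.168
- c = 0.30 gives 6.3/25 = 0.252
- c = 0.40 gives 8.4/25 = 0.336

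The enrolled mean equals 0.2 when c = 0.2 × 25/21 = 0.238. Completer results from 0.20 to just under 0.238 meet the mark while the enrolled mean does not.

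**Step 5. Range over the assumptions.**
- Leavers worsen by 0.3 SD: the limit is (0.2 × 25 + 1.2)/21 = 0.295; c = 0.40 gives (8.4 − 1.2)/25 = 0.288, and c = 0.30 gives (6.3 − 1.2)/25 = 0.204.
- Leavers change as much as completers (l = c): no discrepancy. If they improve more, the discrepancy reverses.
- Share lost, with l = 0: the limit is 0.2/(1 − share), that is 0.211 at 5%, 0.222 at 10%, 0.235 at exactly 15% and 0.267 at 25%.
- Only 2 of the 25 are withdrawals of this kind and other losses resemble completers: 0.2 × 25/23 = 0.217.

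**The case against.** A reader might infer that the plan treats stopping the sessions as leaving the study. The documents do not support that. The no-contact rule is triggered by withdrawal from the study. Unfinished sessions are a protocol variation, after which the end-of-intervention interview is still sought. A Caregiver who gives up after session 2 could be followed under that rule. What stands is that the text does not say which rule applies to an early request to stop, and does not tell the person that assessments may continue.

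A reader might also infer that those who leave are the ones who benefited least. Nothing in the documents shows or quantifies this. It is a reasonable worry, not a finding.

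The remaining objections limit the size of the point. The discontinuation form is not reproduced in the text, so it might hold some outcome items; the only stated purpose, however, is to learn the reason for leaving. The other dyad member can continue, reasons for discontinuation are documented, and missed visits are traced, so departures are not wholly unmeasured. Some of the 15% will be failed contact, which this change would not recover. Someone who leaves after month 3 already has a 3-month score, although whether it is used depends on how the ANOVA treats incomplete cases, which is not stated. Finally, ending contact on request is a proper protection. It should stay for those who want it.

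**Conclusion.** The point holds in a limited form. A participant who asks to leave has one stated path, an exit contact followed by no contact, while a Caregiver who merely runs out of time is still sought for the end-of-intervention interview. Later scores of the first group are lost in a design with no control arm.

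The effect on conclusions is modest. If all 15% attrition is such withdrawal and leavers do not change, the reading against the 0.2 SD mark is wrong only for completer effects from 0.20 to just under 0.238 SD, or just under 0.295 SD if leavers worsen by 0.3 SD. At the effects of 0.3 and 0.4 used in Table 2, the enrolled mean stays above 0.2 in both scenarios. The share attributed to withdrawal and the leavers' change are both assumptions. This does not undermine the feasibility study; it is a gap that is cheap to close beforehand and cannot be repaired afterwards.

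**What to change.** 1. In Withdrawal from the Protocol, ask anyone who wishes to leave which they mean: (a) stopping the sessions only, with the 3- and 6-month assessments kept as scheduled (the Caregiver's by telephone if preferred, as the assessment schedule already allows); or (b) ending all contact, honoured as now. Reserve the no-contact statement for (b). Leave the investigator-initiated withdrawal and Veteran-objection rules as they are.
2. Align Screening and Consent and Measures with this wording, so that it is clear which rule covers an early request to stop.
3. Optionally add to the exit call, dated and voluntary, the Caregiver PHQ-9, GAD-7 and Zarit (9 + 7 + 12 = 28 items) and the Veteran PHQ-9 (9 items). Their timing is irregular, so use them only in a supportive or sensitivity analysis.
4. In Data Analysis, state that all enrolled participants with available data are analysed, for example by a mixed model for repeated measures, with completers only as supportive.

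The cost is a consent and IRB wording amendment and a few extra minutes for about 4 pairs. Some leavers will still decline, so the gap narrows but does not close.

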Caregivers (Intervention): The intervention will be delivered in six individual hour-long sessions during three months by a trained and certified masters-level, mental health professional Program Coach, using the VAMC Memphis Caregiver Center’s national certifying procedures. These include didactic, knowledge test, and supervised role play of intervention components. The first consent and assessment visit will also be in the facility during a patient clinic visit; consent can be obtained by the Research Associate or Program Coach. At this visit, the Program Coach will also begin the Intervention process to establish rapport; subsequent caregiver REACH sessions, approximately every two weeks, will be in the facility, by telephone, or by telehealth, dependent on patient appointments and caregiver desire. All sessions will be taped and treatment fidelity will assess intervention delivery, receipt, and enactment.

STUDY FLOW CHART

First Visit Sequence

Data Collection. A trained masters-level Research Associate will collect data from Caregiver and Veteran by telephone or at clinic visits (which typically occur every three months) at baseline (first assessment and consent visit), end of intervention (3 months), and 6 months.

REACH VA MS STATEMENT OF WORK (SOW)

Task 1: Develop Manual of Operations (MOP)

Month 1

Activities

- Finalize REACH VA MS sessions format
- Finalize REACH VA MS materials
- Finalize screening materials
- Finalize data collection protocol/battery
- Develop and print brochures and posters

Products

- Program Coach notebook, topics and scripts
- Caregiver Notebook
- Screening forms and scripts
- Data collection forms, scripts and documentation
- Brochures and posters

Task 2: IRB approval

Month 1

Activities

- Develop all IRB documents

Products

- IRB study approval

Task 3: Train personnel

Month 1

Activities

- Train Program Coach and research associate

Products

- Trained and certified staff

Task 4: Recruitment and Randomization

Months 1-15

Activities

- Mail brochures

- Telephone and screen potential participants

Products

- Approximately 46 Caregivers/Veterans screened
- 25 pairs recruited

Task 5: Intervention

Months 1-20

Activities

- Schedule and provide intervention for Caregivers

Products

- Intervention sessions provided

Task 6: Data Collection/Data Entry/Cleaning

Months 1-24

Activities

- Collect Caregiver data at baseline, 3 and 6 months
- Collect Veteran data at baseline, 3, and 6 months

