The Research Associate will read the Interviewer Instruction Manual (QxQs) in Manual of Operations Volume II. The Interviewer Instruction Manual will provide general guidelines and specific, question-by-question instructions for completing the REACH VA MS interviews and forms.

MEASURES AND TIME

CAREGIVER

Category	Name of Measure/Form	Citation/Source	Items	When
Demographic information	Participant demographics	various sources	15	Study entry
Health and health services		various sources	17	Study entry Follow up
Depression	Patient Health Questionnaire (PHQ-9)	(Kroenke et al., 2001)	9	Study entry Follow up
Anxiety	Generalized Anxiety Disorder (GAD-7)	(Spitzer et al., 2006)	7	Study entry Follow up
Social Support	Social Support	REACH II	10	Study entry Follow up
Burden	Zarit Burden Interview	(Bedard et al., 2001)	12	Study entry Follow up
Caregiving Tasks	Caregiving Tasks in Multiple Sclerosis Scale (CTiMSS)	(Pakenham, 2007)	24	Study entry Follow up
Risk Assessment	Risk Priority Inventory	Various sources	57	Study entry Follow up

VETERAN

Category	Name of Measure/Form	Citation/Source	Items	When
Demographic information	Participant demographics	various sources	11	Study entry
Health and health services		various sources	6	Study entry Follow up
Depression	Patient Health Questionnaire (PHQ-9)	(Kroenke et al., 2001)	9	Study entry Follow up
Impact on daily life	MS Impact Scale (MSIS-29)	(Riazi et al., 2002)	29	Study entry Follow up
Mobility	Timed Up and Go Test (TUGT)	various sources		Study entry Follow up
Self-Efficacy	MS Self-Efficacy Scale (MSSS)	(Rigby et al., 2003)	14	Study entry Follow up
Fatigue	Modified Fatigue Impact Scale (MFIS)	(Fisk et al., 1994)	21	Study entry Follow up
*Mobility/Neurological exam	Expanded Disability Status Scale (EDSS)	(Kurtzke, 1983)		Study entry Follow up

*Neurological exam completed by physician during clinic appointment.

OUTCOMES

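### The plan is inconsistent on Veteran follow-up mode and clinic interval, so TUGT or EDSS may be missing at 3 or 6 months, and it gives no rule for analysing an incomplete series

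*Combined protocol and SAP*

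**What the plan says.** On follow-up mode, four places bear on the Veteran:

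- Schedule of Data Collection Assessments, Veteran table: "Second (Face to Face) 3 months (+/-14 days" and "Third (Face to Face) 6 months (+/-14 days". In the Caregiver table just above it, telephone is an option at both follow-ups.
- Measures, directly below those tables: "Data collection will occur at baseline, End of Intervention (3 months), and 6 months either face to face or by telephone". No distinction is drawn between the two groups.
- Data Collection (under Research Methods): the Research Associate will "collect data from Caregiver and Veteran by telephone or at clinic visits (which typically occur every three months"). Here the Veteran is named.
- Retention Procedures: "All Caregivers/Veterans get phone reminders prior to their scheduled data collection telephone calls".

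On EDSS, the footnote to the Veteran table in Measures and Time reads "Neurological exam completed by physician during clinic appointment". TUGT carries no such footnote. The Data Collection paragraph puts clinic visits at about three months, but the Recruitment section says "Veterans with MS are only seen in the MS clinic every three to six months" and warns that this could cause enrollment to be missed. The baseline visit takes place during a clinic visit.

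On analysis, the Data Analysis section states that the primary outcomes are measured for everyone at all three time points and specifies repeated measures ANOVA. Data Types and Coding for Missing Data gives entry codes for missing values. The available text gives no rule for analysing a participant who lacks one visit.

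**The concern.** TUGT is a timed physical task and EDSS a neurological examination, so neither can be obtained by telephone. Staff who follow the Data Collection paragraph or Retention Procedures could complete a Veteran follow-up as those sections describe and still have no function data.

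Following the face-to-face table removes that risk for TUGT but not for EDSS, which also needs a physician and a clinic appointment near the due date. No section provides an extra appointment for a Veteran seen less often than every three months.

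The analysis is written as if every series were complete. With 25 pairs planned, each Veteran dropped for one absent value is a noticeable loss on TUGT and EDSS, the only two outcomes listed as Veteran function.

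**Working it through.** **1. Can a clinic-bound EDSS fall inside the windows?** Take baseline at a clinic visit and a fixed interval afterwards. With 30.4 days to the month, 14 days is about 0.46 month, so the windows run from about 2.5 to 3.5 and from 5.5 to 6.5 months.

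| Clinic interval (months) | Visits after baseline (months) | In 3-month window | In 6-month window |
|---|---|---|---|
| 3 | 3, 6 | yes | yes |
| 4 | 4, 8 | no | no |
| 5 | 5, 10 | no | no |
| 6 | 6 | no | yes |

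All four intervals lie in the range given under Recruitment. Only the three-month interval in the Data Collection paragraph supplies both EDSS values. The six-month interval loses one, and the four- and five-month intervals lose both.

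**2. The plan's own sample-size figures.** Table 2 covers Caregiver outcomes only. With the reliability r used as the correlation between visits, the SD of change in SD units is √(2(1−r)), and the paired sample size is 2(1−r)(1.960+0.842)²/d², rounded up. Doubling that and dividing by 0.85 (rounded up) gives:

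| Outcome | r | Paired n at d = 0.3 / 0.4 | Doubled, ÷ 0.85 | Table 2 |
|---|---|---|---|---|
| PHQ-9 | 0.84 | 28 / 16 | 66 / 38 | 66 / 38 |
| GAD-7 | 0.83 | 30 / 17 | 71 / 40 | 71 / 40 |
| Zarit | 0.88 | 21 / 12 | 50 / 29 | 50 / 29 |

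All six entries reproduce. The doubling is not explained, though 50 subjects fits 25 pairs counted as two people each. There is no corresponding figure for TUGT or EDSS, so there is no Veteran power statement to correct.

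**3. Illustration of the loss under casewise deletion.** Inputs from the plan: 25 pairs, 15% attrition, α = 0.05 (taken as two-sided, which reproduces Table 2). Expected Veteran completers: 25 × 0.85 = 21.25, so 21. Assumed, because the plan gives neither: the share of completers lacking a value, and r for TUGT and EDSS (0.84, borrowed from the Caregiver PHQ-9 row, and 0.70). The detectable d gives 80% power in a paired t-test with n−1 degrees of freedom and noncentrality d√n/√(2(1−r)). Complete cases are 21.25 × (1 − share), rounded down.

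| Assumed share missing | Complete cases | Detectable d, r = 0.84 | Detectable d, r = 0.70 | Power at d = 0.4, r = 0.84 |
|---|---|---|---|---|
| 0% | 21 | 0.36 | 0.50 | 87% |
| 10% | 19 | 0.38 | 0.53 | 83% |
| 25% | 15 | 0.44 | 0.60 | 72% |
| 50% | 10 | 0.56 | 0.77 | 51% |

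The table applies a two-visit contrast to the cases left after three-visit deletion. A direct baseline-to-6-month comparison would not lose a Veteran who lacked only the 3-month value.

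**The case against.** The strongest reply is that the only Veteran-specific schedule is unambiguous. It requires face-to-face visits at 3 and 6 months, and the general Measures sentence below it can be read as covering both groups loosely. This stands in part. It shows that the plan does not simply permit telephone follow-up of Veterans, and that TUGT is safe if the table is followed. It does not remove the Data Collection paragraph, which names the Veteran, or the Retention Procedures wording.

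Second, nothing bars staff from booking the 3-month visit as a clinic appointment, and an assessment outside 14 days is logged as a protocol variation; no section says it is discarded. That also stands. But the plan neither says that such bookings will be made nor says whether a late EDSS counts as the scheduled value.

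Third, casewise deletion is the usual ANOVA default, not something that the Data Analysis section states. This is correct, and the gap is the absence of any rule.

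A reader might go further and infer three things that the documents do not support:

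- That values will certainly be missing. The share on longer intervals is not given, and TUGT is at risk only if telephone is used.
- That Veterans seen less often are the more stable ones, so that complete cases are a selected group. Nothing says what determines the interval.
- That TUGT and EDSS carry Hypothesis 1. They are listed with other Veteran outcomes and none is given priority.

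It is also tempting to make baseline to 6 months the main EDSS contrast. As the interval table shows, that does not secure the value for Veterans seen every four or five months.

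**Conclusion.** The point holds as an inconsistency with a possible cost. The sections conflict on how Veterans are followed up and on how often they attend clinic. EDSS may therefore be absent at 3 months, and on some intervals at 6 months as well; TUGT may be absent if the telephone wording is followed. The plan does not say how an incomplete series is analysed.

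The size cannot be fixed from the documents. Across assumed missing shares of 0 to 50%, complete Veteran cases fall from 21 to 10, and the detectable effect rises from 0.36 to 0.56 SD at r = 0.84, or from 0.50 to 0.77 SD at r = 0.70. Those figures rest on casewise deletion and on assumed shares and correlations, and should be read as illustrative. The changes are worth making because they are cheap and the sample is small.

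**What to change.** 1. Amend the Data Collection paragraph, Retention Procedures and the Measures sentence so that Veteran TUGT is collected face to face at 3 and 6 months, as the schedule table already requires. Keep telephone for Caregivers and, if needed, for Veteran questionnaires.
2. In Data Analysis, replace repeated measures ANOVA with a linear mixed model for repeated measures that uses all available visits, so that a Veteran who lacks one visit still contributes.
3. Reconcile the two statements of the clinic interval. Enter off-window EDSS values in the model at their actual assessment date, with time since baseline as the time variable. Step 2 alone does little for a Veteran seen every four or five months, who would otherwise contribute only a baseline EDSS.

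The cost is a few sentences of wording and slightly more analysis work. The model assumes that missing values are missing at random given the observed data, which should be stated in the plan. No additional physician visit is required, but a Veteran with no clinic appointment near a due date will still have no EDSS close to that time.
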